5.1 Variables

The following pharmacokinetic parameter will be determined using the actual recorded sampling times with Phoenix WinNonlin (Version 6.4 or higher): Cmin. PK samples will be collected on Days 1, 29, 85, and at EOS.

5.2 Descriptive analyses

AIN457 serum concentration data will be listed by treatment, patient, and visit/sampling time point. Descriptive summary statistics will be provided by treatment and visit/sampling time point, including the frequency (n, %) of concentrations below the LLOQ and reported as zero.

Summary statistics will include mean (arithmetic and geometric), SD, CV (arithmetic and geometric), median, minimum and maximum. Concentrations below LLOQ will be treated as

zero in summary statistics and for PK parameter calculations. A geometric mean will not be reported if the dataset includes zero values. Pharmacokinetic parameters will be calculated and will be listed by treatment and patient.

6 Statistical methods for efficacy parameters

Baseline is defined as day 1 or if data is missing at day 1 then the last non-missing pre-dose value will be used as the baseline.

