2.2 Secondary objective(s)

Objective	Endpoint

To assess the efficacy of secukinumab 300 mg s.c. vs. placebo in patients with overuse rotator cuff tendinopathy in relieving symptoms over time	
WORC score at Weeks 2, 4, 8, 12, 18 and 24Disability of Arm, Shoulder and Hand Questionnaire (QuickDASH) score at Weeks 2, 4, 8, 12, 14, 18 and 24American Shoulder and Elbow Surgeons Shoulder Evaluation Form (ASES) score at Weeks 2, 4, 8, 12, 14, 18 and 24EQ5D-5L score at Weeks 2, 4, 8, 12, 14, 18 and 24Pain score using a VAS scale (considering the last 24 hours) at Weeks 2, 4, 8, 12, 14, 18 and 24Patient global assessment (PGA) score using a VAS scale (considering the last 24 hours), at Weeks 2, 4, 8, 12, 14, 18 and 24Physician global assessment (PhGA) score using a VAS scale (considering the last 24 hours), at Weeks 2, 4, 8, 12, 14, 18 and 24

To assess the structural changes in the rotator cuff tendinopathy over time	
MRI Sein score at Weeks 8, 14 and 24

To assess PK/immunogenicity in secukinumab treated patients	
PK/immunogenicity assessment at Day 1, Weeks 4, 12, 24

To confirm the safety and tolerability of AIN457 in patients with overuse rotator cuff tendinopathy over time	
Safety and tolerability assessments over time: Incidence and severity of AEs and SAEs; routine safety laboratory parameters

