6.2 Treatment arms

Patients will be assigned to one of the following 2 treatment arms in a 1:1 ratio, with approximately 50 patients per arm.

- Group 1: Secukinumab 300 mg s.c. (2 x 150 mg)
- Group 2: Placebo s.c. (2 injections)

Treatment is administered at Day 1 (randomization visit), and Weeks 1, 2, 3, 4, 8 and 12.

Subjects who complete the assessments associated with Week 14 visit should continue the study in a (treatment free) follow up period of 10 weeks up to 24 weeks.

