8.1 Assessment schedule

Subjects should be seen for all visits/assessments as outlined in the assessment schedule, [Table 8-1](#), or as close to the designated day/time as possible.

Missed or rescheduled visits should not lead to automatic discontinuation. Subjects who prematurely discontinue the study for any reason should be scheduled for a visit as soon as possible, at which time all of the assessments listed for the final visit will be performed. At this final visit, all dispensed investigational product should be reconciled, and the adverse event and concomitant medications recorded on the CRE.

Table 8-1 Assessment schedule

Epoch	Screening			Treatment								Follow-up	
Visit Name	Screening	Run-in ²	Baseline	Treatment								Follow-up	EOS
Visit Numbers ¹	1	2	3	101	102	103	104	105	106	107	199	201	299
Days	-49 to -22	-21 to -8	-7 to -1	1	8	15	22 ±1	29 ±1	57 ±2	85 ±2	99 ±2	127 ±7	169 ±7
Weeks of dosing	-	-	-	0	1	2	3	4	8	12	14	18	24
Chest X-Ray ⁷			S										
Randomization				X									
Study drug administration ⁴				X	X	X	X	X	X	X	X		
Physiotherapy		S ¹³						S					
Physical Examination ⁵	S		S										S
Body Height ⁵	X												
Body Weight ⁵	X		X										X
Body Temperature ⁵	X		X	X		X		X	X	X	X		X
Blood Pressure and Pulse Rate ⁵	X		X	X		X		X	X	X	X		X
Electrocardiogram (ECG) ⁵	S		S									S	S
Hematology ⁵	X		X						X			X	X
Clinical Chemistry ⁵	X		X						X			X	X
Urinalysis ⁵	X		X									X	X
Lipid panel and glucose ⁵			X									X	
Shoulder X-Ray ^{6, 12}			S										
Shoulder US	S												
Shoulder MRI			X ¹²							X	X		X

Epoch	Screening			Treatment								Follow-up		
	Visit Name	Screening	Run-in ²	Baseline	Treatment								Follow-up	EOS
Visit Numbers ¹	1	2	3	101	102	103	104	105	106	107	199	201	299	
Days	-49 to -22	-21 to -8	-7 to -1	1	8	15	22 ±1	29 ±1	57 ±2	85 ±2	99 ±2	127 ±7	169 ±7	
Weeks of dosing	-	-	-	0	1	2	3	4	8	12	14	18	24	
PD blood (IL-17A) ⁵				X				X		X				X
Commercially Confidential Information														
PK blood collection ⁵					X				X		X			X
Commercially Confidential Information														
Immunogenicity ⁵					X							X		X
Commercially Confidential Information														
Concomitant medications												X		
Adverse Events												X		
Comments												X		
Study completion information														X

¹ Visit structure given for internal programming purpose only

² Run-in to standardize physiotherapy and stabilize NSAIDS, no site visit required

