³ Serum pregnancy test required as Screening and EOS, for remaining visits: urine test

⁴ At study days 8 and 22 study medication can be administered by study nurse at patients home

⁵ Collected pre-dose if applicable

⁶ Historic data accepted if obtained ≤3 months before baseline

⁷ A chest X-ray (can be replaced by historic CT or MRI) is required if it was not performed and evaluated within 3 months prior to screening. The X-ray should be performed after it is certain the subject meets other inclusion/exclusion criteria in order to minimize unnecessary exposure to radiation.

⁸ To be done the night before and the night after each visit (except for EOS when it is done only before the visit).

⁹ Commercially Confidential Information

¹⁰

¹¹ The PPD skin test can be performed at any time during the screening period, but it must be read within 72 hours and before randomization

¹² Assessments to be performed maximum 14 days before study Day 1

¹³ Duration of the standardized physiotherapy might be prolonged if required by local regulations

S: collected as source data only

For all subjects who discontinue from the study, the investigator should ensure that the subject completes the end of treatment visit (EOS) 4 weeks after last study treatment of secukinumab. Every attempt should be made to obtain MRI images at the final visit, unless the MRI was taken within 8 weeks before discontinuation.

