Safety assessments will include physical examinations, ECGs, vital signs, standard clinical laboratory evaluations (hematology, blood chemistry, and urinalysis), adverse event and serious adverse event monitoring.

Figure 1-1 Study design

2 First interpretable results (FIR)

Commercially Confidential Information

3 Interim analyses

Commercially Confidential Information

4 Statistical methods: Analysis sets

For patients for which the actual treatment received does not match the randomized treatment the treatment actually received will be used for the analysis.

The safety analysis set will include all patients that received any study drug.

The PK analysis set will include all patients with at least one available valid (i.e. not flagged for exclusion) PK concentration measurement, who received any study drug and experienced no protocol deviations with relevant impact on PK data.

The PD analysis set will include all patients with any available PD data, who received any study drug and experienced no protocol deviations with relevant impact on PD data.

For efficacy data summaries and statistical analyses for the Day 127 visit, only patients who have completed the treatment Epoch will be included. For Day 169, only patients who have completed the treatment Epoch and have completed the Follow-up Epoch will be included.

The analysis sets and protocol deviation codes are related as follows:

Table 4-1 Protocol deviation codes and analysis sets

Category	Text description of deviation	Data exclusion
Deviation code		
Patients are excluded from PK analysis in case of these PDs:		
INCL01	Written informed consent was not obtained before any study assessment was performed	Exclude patient from PK analysis set Yes
Patients are excluded from PD analysis in case of these PDs:		
INCL01	Written informed consent was not obtained before any study assessment was performed	Exclude patient from PD analysis set Yes
INCL3B	Patient did not fulfil the following: Tendinopathy with no more than a 50% tear as established by ultrasound at screening (historic data acceptable if not older than 3 months) and MRI at baseline: Sein MRI tendinopathy scoring system grade I-III; with no tear or partial tear [maximum 50% tendon thickness (Bauer tendon thickness score maximum 2); AP length maximum 10 mm (Bauer tendon length score max 2)]. Maximum 50% of patients with partial tear	Exclude patient from PD analysis set

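### The last PK summary point in SAP 5 is labelled only EOS, so the descriptive Week 24 concentration row can mix samples taken at different times since the last dose

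*SAP*

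**What the plan says.** **Sampling.** SAP 5.1: "PK samples will be collected on Days 1, 29, 85, and at EOS". Only the last occasion has no day number. The endpoint in Protocol 2.2 is fixed in time: "PK/immunogenicity assessment at Day 1, Weeks 4, 12, 24".

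**Summaries.** SAP 5.2: "Descriptive summary statistics will be provided by treatment and visit/sampling time point". The visible text of SAP 5 contains no visit window, no early-termination category and no rule based on time since dose. Actual times are mentioned in SAP 5.1 only for the PK parameter Cmin, which "will be determined using the actual recorded sampling times".

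**Dosing.** Protocol 6.2: "Treatment is administered at Day 1 (randomization visit), and Weeks 1, 2, 3, 4, 8 and 12". Table 8-1 places the scheduled EOS visit at Day 169 (±7), Week 24.

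**EOS after discontinuation.** The text under Table 8-1 asks that a patient who discontinues "completes the end of treatment visit (EOS) 4 weeks after last study treatment of secukinumab". The opening of Protocol 8.1 asks for a visit as soon as possible, "at which time all of the assessments listed for the final visit will be performed", and Protocol 7.2 also asks for EOS as soon as possible after the drug is stopped. Table 8-1 includes PK blood at EOS.

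**Restrictions.** SAP 4: "For efficacy data summaries and statistical analyses for the Day 127 visit, only patients who have completed the treatment Epoch will be included". The next sentence adds, for Day 169, completion of the follow-up epoch. The PK analysis set needs one valid concentration, some study drug and no deviation with relevant impact on PK data. The only deviation that Table 4-1 maps to PK exclusion is INCL01 (consent).

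**The concern.** EOS is a visit name, not a time since dose. A completer's EOS sample shows what remains 12 weeks after the last injection. The EOS sample of a patient who stops early is usually taken sooner. If both fall in one row, its mean describes neither situation.

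PK is a named secondary objective, with Week 24 as one of its time points. Protocol 3.3 justifies the 12 weeks off treatment as a period in which to observe relapse and safety, and Protocol 1.1 says that the data are to support Phase III planning. Residual drug at Week 24 helps in reading off-treatment results, so an overstated value could mislead. For efficacy, SAP 4 already confines these late visits to completers.

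**Working it through.** **1. The plan's own interval.** Day 169 − Day 85 = 84 days = 12.0 weeks, which agrees with the stated 12-week follow-up after last treatment. With the visit windows (±7 and ±2 days) the range is 75 to 93 days, or 10.7 to 13.3 weeks.

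**2. The interval for patients who discontinue.** Under the note to Table 8-1 it is 28 days. Under Protocol 7.2 and the opening of 8.1 it is not fixed. It can also exceed 28 days: Protocol 7.2 stops treatment after two missed doses, so a patient who misses Weeks 8 and 12 is already 8 weeks past the Week 4 dose. A patient who leaves during follow-up after the Week 12 dose can be sampled up to nearly 12 weeks after it.

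**3. Could the two kinds of sample meet in one row?** SAP 5.1 gives both the label EOS, SAP 5.2 summarises by visit/sampling time point, the completer rule in SAP 4 is introduced for efficacy, and early stopping is not a listed PK exclusion. Nothing visible separates them.

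**4. Size, under stated assumptions.**

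Inputs from the documents:
- Equal doses on Days 1, 8, 15, 22, 29, 57 and 85 (Protocol 6.2, Table 8-1).
- About 50 patients per arm (Protocol 6.2).
- 40 per arm completing Week 14 (Protocol 11.7), a gap of 10.

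Assumptions:
- One-compartment decay, with half-life h as an assumed value because the human PK section is redacted.
- Discontinuers sampled 28 days after their last dose.
- Stopping after 1, 2, 3, 4, 5 or 6 doses equally weighted.

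Formulas:
- Concentration at day t, up to a constant: C(t) = Σ 2^(−(t − dose day)/h) over the doses received.
- Ratio for a patient who stops after n doses: r(n) = C(day of dose n + 28, n doses) / C(169, 7 doses).
- Pooled mean relative to the completer mean, with m of 50 early samples: [(50 − m) + m × mean r] / 50.

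Example, h = 20 days:
- Completer: 0.0030 + 0.0038 + 0.0048 + 0.0061 + 0.0078 + 0.0206 + 0.0544 = 0.1005.
- One-dose stopper: 2^(−28/20) = 0.379, so r(1) = 0.379/0.1005 = 3.77.
- r(1) to r(6): 3.77, 6.73, 9.05, 10.87, 12.30, 8.43; mean 8.52.
- 5 of 50: (45 + 5 × 8.52)/50 = 1.75.
- 10 of 50: (40 + 10 × 8.52)/50 = 2.50.

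| Assumed half-life (days) | Range of r(1) to r(6) | Mean r | Pooled/completer, 5 of 50 | Pooled/completer, 10 of 50 |
|---|---|---|---|---|
| 14 | 11.2 to 31.5 | 22.4 | 3.14 | 5.28 |
| 20 | 3.77 to 12.30 | 8.52 | 1.75 | 2.50 |
| 28 | 1.66 to 6.04 | 4.15 | 1.31 | 1.63 |
| 30 | 1.43 to 5.33 | 3.65 | 1.27 | 1.53 |
| 42 | 0.78 to 3.14 | 2.15 | 1.12 | 1.23 |
| 56 | 0.52 to 2.21 | 1.52 | 1.05 | 1.10 |

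Averaged over stopping points, the pooled mean is raised at every half-life tried. For an individual the ratio can fall below 1: at 42 days or longer, a patient who stops after one dose has less drug than a completer.

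**The case against.** **Pooling is not instructed.** A reader might infer that the SAP orders summaries by nominal visit. It does not use that word, and a programmer could take EOS to mean Day 169 only, as in Table 8-1. The Day 169 sentence in SAP 4 does not itself repeat the word efficacy. Protocol 11.5.3 is redacted and could hold a rule, and samples can be flagged for exclusion by criteria that are not shown. All this stands as far as it goes: the fault is an absent rule, not a wrong one. But SAP 5, which implements the analysis, is visible and leaves the choice open.

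**Early EOS is not always 4 weeks or less after dosing.** A reader might infer this from the note to Table 8-1, but step 2 shows later samples are possible. This narrows the contrast for some patients and makes the row more heterogeneous.

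**The size is easily overstated.** Taking only patients who stop after the Week 4 or Week 8 dose at 20 to 30 days gives individual ratios of 4.2 to 12.3. Those are high-exposure stopping points, and a one-dose stopper has 1.4 to 3.8. Ten of 50 is an upper bound: the gap between 50 and 40 covers all non-completion by Week 14, and patients who withdraw consent or are lost give no EOS sample.

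**The harm is limited.** SAP 5.2 also reports median, minimum and maximum, lists every concentration, and drops the geometric mean if any value is zero. That stands.

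**Two extensions fail.** A reader might want Day 29 or Day 85 values excluded after a missed dose. Averaging concentrations as actually dosed is legitimate, so that is a preference. A reader might also infer that a pooled Week 24 antibody result is distorted, but antibody results are only listed.

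**Conclusion.** The concern holds in limited form. As written, the plan lets early-termination EOS samples enter the same descriptive PK row as true Week 24 samples, because the completer rule introduced for efficacy in SAP 4 has no PK counterpart. The likely direction is upward.

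The size cannot be established from the documents. Under the assumptions in step 4, the pooled arithmetic mean is about 1.3 to 1.75 times the completer mean with 5 of 50 early samples and 1.5 to 2.5 times with 10 of 50 at a half-life of 20 to 30 days. It is about 1.1 to 1.2 times with 10 of 50 at 42 to 56 days. With no early EOS samples there is no effect.

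Only a descriptive secondary summary is affected; the primary analysis and the individual listings are not. A reader might infer that the Week 24 level will certainly be inflated several-fold. The documents do not support that, since the half-life, the doses received and the number of early EOS samples are all unknown.

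**What to change.** In SAP 5.1 and 5.2, define the last PK summary time point as Week 24 (Day 169 ± 7) and restrict it to patients who completed both the treatment and follow-up epochs, matching the Day 169 rule in SAP 4. List EOS samples from patients who ended early, and show them in a separate early-termination row with time since last dose.

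Separately, Protocol 7.2, the opening of 8.1 and the note under Table 8-1 give conflicting timings for the early EOS visit and must be reconciled. The SAP change works whichever timing is kept.

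The cost is a few lines of SAP text and one derived variable, from dosing dates and times that Protocol 8.5.4 already has recorded. No new samples are needed. The downside is slightly fewer values in the Week 24 row.

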6.1 Primary objective

The primary aim of this study is to assess the efficacy of secukinumab 300 mg s.c. vs. placebo in patients with overuse rotator cuff tendinopathy in relieving clinical symptoms at week 14.

6.1.1 Variable

The primary variable, the WORC score, will be available at pre-dose, day 1 and weeks 2, 4, 8, 12, 14, 18 and 24. The total score and the subscores will be included in the summaries and statistical analyses detailed in the following sections and will take the form of percentage of normal scores derived as:

- Physical symptoms score = (600-sum of Physical symptoms answers)/6
- Sports and Recreation score = (400-sum of Sports and Recreation answers)/4
- Work score = (400-sum of Work answers)/4
- Lifestyle score = (400-sum of Lifestyle answers)/4
- Emotions score = (300-sum of Emotions answers)/3
- Total score = (2100-sum of all answers)/21

If there are <=2 missing values in a domain, the domain score can be calculated using the average of the other items in the domain. If there are more than 2 missing items in a domain, the concerning WORC questionnaire is considered incomplete and is excluded from the analyses.

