8.6.1.1 The WORC score

The WORC score is a patient reported outcome tool, uniquely developed for the rotator cuff diseases by Kirkley and co-workers ([Kirkley et al 2003](#)). The WORC is self-administered and consists of 21 items divided into five domains: Physical Symptoms (6 items); Sport/Recreation (4 items); Work Function (4 items); Lifestyle Function (4 items) and Emotional Function (3 Items). Items are scored by a 10 cm VAS so the best possible result is 0 (asymptomatic patient) while the worst possible result is 2100 (highly symptomatic). The WORC Index has a recall period of 1 week and is filled in by the patient at the clinic at visits specified in the [Assessment schedule](#).

Details of the WORC are outlined in the SOM.

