6.1.3 Statistical model, assumptions and hypotheses

The primary end-point (change from baseline in WORC score at Week 14) will be analyzed by repeated measures analysis of covariance including all WORC scores available. The change at Week 14 will be compared between treatments to address the primary objective.

The baseline WORC score will be included as a covariate. The stratification factors partial tear/no tear and previous steroid injection (yes/no) will be included in the model as fixed effects along with fixed effects for treatment, timepoint and the treatment by timepoint interaction. An unstructured within-patient covariance will be considered.

The number of covariance and mean parameters may be reduced by model comparison tools such as the BIC criterion for model fit. Missing variables will be considered missing at random.

The adjusted mean of treatment effect at Week 14 as well as the difference between treatment arms will be reported along with a 95% one-sided (90% two-sided) confidence interval.

The primary analysis will also be repeated for patients where the affected arm is the dominant arm.

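### SAP 6.1.1 removes the whole WORC questionnaire when one domain fails, so complete subscores are lost, and its fixed limit of two blanks treats domains of different length unevenly

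*SAP*

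**What the plan says.** Protocol 8.6.1.1 gives the domains as "Physical Symptoms (6 items); Sport/Recreation (4 items); Work Function (4 items); Lifestyle Function (4 items) and Emotional Function (3 Items"), 21 items in all. SAP 6.1.1 defines five domain scores and a total, each as a percentage of normal, and sends all six into the summaries and statistical analyses. The shortest domain is "Emotions score = (300-sum of Emotions answers)/3", and the total is "Total score = (2100-sum of all answers)/21".

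The completeness rule has two parts. First: "If there are <=2 missing values in a domain, the domain score can be calculated using the average of the other items in the domain". Second: "If there are more than 2 missing items in a domain", then "the concerning WORC questionnaire is considered incomplete and is excluded from the analyses". The unit removed is the questionnaire, not the domain. No minimum share of a domain and no minimum number of items overall is stated.

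SAP 6.1.3 gives the use of the score: "The primary end-point (change from baseline in WORC score at Week 14) will be analyzed by repeated measures analysis of covariance", with all available WORC scores included and missing values taken as missing at random. Protocol 8.6.1 has the study coordinator check questionnaires for completeness and encourage patients to fill in gaps.

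**The concern.** Two features of the rule do not fit the planned subscore analyses.

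The first is the unit of deletion. A subscore depends only on its own items, so blanks in Work say nothing about whether Physical symptoms, Sports, Lifestyle or Emotions were properly measured. Yet three Work blanks delete all of them. If this happens on Day 1, the baseline for every subscore falls back to an earlier pre-dose value under SAP section 6, or is missing if there is none.

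The second is the fixed count. Two blanks are a third of a 6-item domain, half of a 4-item domain and two thirds of the 3-item domain. The rule is most lenient where there is least information. What is at stake is the completeness and precision of the subscore results.

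**Working it through.** **Inputs.** Items per domain: 6, 4, 4, 4, 3 (Protocol 8.6.1.1). Limit of two blanks per domain, and deletion of the questionnaire beyond it (SAP 6.1.1). Planning SD of change: 34 points (Protocol 11.7). The plan gives no figure for missing items. Its own item count reproduces: 6 + 4 + 4 + 4 + 3 = 21, and 21 × 100 = 2100, the worst raw score.

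**Step 1: what the rule accepts.**

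| Domain | Items | Fewest answers accepted now | Share | Fewest under an at-least-half rule |
|---|---|---|---|---|
| Physical symptoms | 6 | 4 | 67% | 3 |
| Sports, Work, Lifestyle (each) | 4 | 2 | 50% | 2 |
| Emotions | 3 | 1 | 33% | 2 |

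**Step 2: what one failed domain removes.** Three blanks in one domain and none elsewhere leave 21 − 3 = 18 answers and four complete domains. All are excluded. There are 20 such patterns in Physical symptoms, 4 in each 4-item domain and 1 in Emotions: 20 + 3 × 4 + 1 = 33 of the 1,330 ways to leave three items blank.

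**Step 3: precision of a subscore.** If a domain of k items is scored from the mean of m answers, the error variance against the full-domain score is s² × (1/m − 1/k), where s² is the within-domain item variance.

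- Emotions, 1 of 3 (kept): 1 − 1/3 = 0.67 s²
- Emotions, 2 of 3: 1/2 − 1/3 = 0.17 s²
- Physical symptoms, 3 of 6 (rejected): 1/3 − 1/6 = 0.17 s²

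The kept Emotions score has 0.67 / 0.17 = 4 times the error variance of the rejected Physical score. The ratio needs only equal s² in the two domains. To put it in points, assume an item SD of 25 and an inter-item correlation of 0.6, so that s² = 625 × 0.4 = 250. The error SD is √(250 × 2/3) = 12.9 for Emotions on one answer and √(250/6) = 6.5 for the other two cases. Over correlations of 0.4 to 0.8 the pair runs from 15.8 and 7.9 down to 9.1 and 4.6.

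**Step 4: why the half rule should not govern the total.** This step assumes that blanks enter the total through their own domain average, which SAP 6.1.1 does not state. The error variance of the 21-item sum is then the sum over domains of k² × s² × (1/m − 1/k).

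- Thinnest form kept now, 4+2+2+2+1 = 11 answers: 3 + 4 + 4 + 4 + 6 = 21 s². Error SD of the total: √(21 × 250)/21 = 3.5 points.
- Thinnest form under a half rule, 3+2+2+2+2 = 11 answers: 6 + 4 + 4 + 4 + 1.5 = 19.5 s², or 3.3 points.
- Physical 3 of 6, otherwise complete: 36 × 1/6 = 6 s². Emotions 1 of 3, otherwise complete: 9 × 2/3 = 6 s². Both give 1.8 points.

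If every domain had to pass the half rule, the total would still admit 11 of 21. A form with 19 of 21 answered (two Emotions blanks) would newly lose its total. Forms with three blanks in a 4-item domain would gain nothing. One pattern would be exchanged for another of equal error variance.

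**The case against.** The rule is explicit, prespecified and the same in both arms, and any completeness threshold is partly convention. The coordinator's check should make forms with three blanks in one domain uncommon. The Protocol refers WORC details to the Site Operations Manual, and Protocol 11.4.3 on missing values is redacted, so supporting reasoning may exist out of sight. All of this stands, and it limits the size of the point. None of it gives a reason to delete a fully answered domain because another one failed.

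A reader might go further and infer that the primary result is damaged, because an 18-of-21 total can be discarded while an 11-of-21 total is kept. The counts are right. For three blanks in Physical symptoms or a 4-item domain, the discarded total would also be the more precise one (1.8 or 2.6 points against 3.5, on the Step 4 assumptions; 2.6 is √(12 × 250)/21). If the three blanks are the whole Emotions domain, nothing in that domain remains to average, and exclusion is defensible. These are extremes of unknown frequency. Even the thinnest kept total adds only about (3.5/34)² = 1% to the planning variance.

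A reader might also convert discarded Week 14 forms into lost patients and quote a fall in power. The documents do not support that: they give no missing-item rate, and under SAP 6.1.3 a patient with a missing visit still contributes other visits. The suggestion that people who do not work or play sport leave those domains blank, so that deletion selects patients, is conjecture. Nothing in the documents shows that it happens.

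**Conclusion.** The concern holds for the subscores. Deleting the questionnaire discards up to four complete domain scores for a fault in a fifth. The fixed limit also accepts an Emotions score with four times the error variance of a Physical score that it rejects. The deletion follows from the text alone. The fourfold ratio assumes equal within-domain item variance, and the values in points also rest on the assumed SD and correlations.

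The practical effect is probably small and cannot be sized from the documents. The case for changing the primary total's main rule is not made. This is an inexpensive improvement to the SAP, not a threat to the primary conclusion.

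**What to change.** In SAP 6.1.1, before unblinding:

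1. When a domain fails, set only that subscore to missing and keep the other subscores from the same questionnaire.
2. Score a domain from the mean of its answered items when at least half are answered: 3 of 6, 2 of 4, 2 of 3.
3. State that items 1 and 2 apply to the subscores only. Keep the current rule for the primary total.
4. Add a sensitivity analysis of the primary endpoint that retains totals meeting an overall minimum number of answered items. Fix that number in advance, and state how blanks enter the total, including a domain with no answers.

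The cost is a few lines of SAP wording and derivation code and one extra model run. Emotions subscores resting on a single answer would be dropped. The totals on those forms are unaffected, because the domain rule does not reach them.
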